- 24. To include color, appearance, glucose, bilirubin, ketone, specific gravity, blood, pH, protein, urobilinogen, nitrite, leukocyte esterase. If warranted by dipstick analysis, microscopic analysis to include RBC, WBC, casts, crystals, epithelial cells, and bacteria. Will be performed at screening, and when clinically indicated.
- 25. For POCBPs only.
- 26. CA19-9 will be measured from blood collected at screening (post-operative measurement required within 3 weeks of C1D1), C1D1, during PK sampling, on days of BNT321 administration and at disease assessment time points detailed in Footnote 25. During BNT321 monotherapy every 3 months (12 weeks), every 2 years (±7 days), and then every 6 months for 3 years. For all collections on BNT321 administration days, blood will be collected both pre-infusion and post-infusion (end of infusion [EoI] +5 min [± 5 min]). For further details, refer to Table 3.
- 27. For a full pharmacokinetic profile and in-depth sampling, blood will be collected on C2D3 and C3D3, (pre-infusion, EoI +5 min] ± 5 min], EoI +1 h [±15 min] and EoI +4 h [±30 min]). For Cycles 4 onwards, only C_{trough} (pre-infusion) and C_{max} (EoI +5 min [±5 min]) will be drawn on day of BNT321 administration. All other timepoints will include only one blood draw timepoint per day. For further details, refer to Table 3.
- 28. Disease assessment will consist of imaging by CT/MRI scan and serum CA19-9 and will be performed at screening (baseline post-operative imaging within 4 weeks of C1D1 and serum CA19-9 within 3 weeks of C1D1 are required), and then after C1D1 every 3 months (12 weeks) for 2 years and then every 6 months for 3 years (±7 days). CT with contrast or MRI (as appropriate for patient, or multiparametric MRI following an inconclusive CT). Patients should be evaluated with the same imaging method (CT or MRI) throughout the trial.
- 29. Anti-drug antibodies will be measured from blood collected prior to dosing of mFOLFIRINOX on C1D1, C3D1, C6D1, and at EOT.
- 30. ADCC, CDC and cytokines will be measured from blood collected prior to dosing of mFOLFIRINOX and/or BNT321 on days of trial drug administration. Collected on the following days: C1D1, C2D3, C2D8, C4D3, C4D8, C16D1 and C16D5. For Cycle 4 collections, should be adjusted to C4D1 and C4D5 if BNT321 administration is given on C4D1. Whole blood collected for PBMC isolation for ADCC assessment will only be collected if logistically manageable.

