	0,	Day 1	Predose	Eol +5 min [±5 min]	Eol +30 min [±5 min]	Eol +1 h [±5 min]	Eol +4 h [±30 min]	Day 8	Predose	Eol +5 min [±5 min]	
Blood sample for BNT321 pharmacokinetics			х	Х	х	х	Х	Х	х	х	
Blood sample for CA19-9	Х	Х	Х	Х				X*	Х	Х	

Assessment for Randomized Phase II-		Cycle 1			Cycle 2-	3			Су	rcle 4–24
combination arm only (mFOLFIRINOX + BNT321)	SCR			Day o	of BNT321 adminis	stration		_	Day of BNT321 administration	
	0,	Day 1	Predose	Eol +5 min [±5 min]	Eol +30 min [±5 min]	Eol +1 h [±5 min]	Eol +4 h [±30 min]	Day 8	Predose	Eol +5 min [±5 min]
Blood sample for BNT321 pharmacokinetics			х	Х		х	х	X*	X**	X**
Blood sample for CA19-9	Χ	Х	Х	Х				X*	X**	X**

Eol = end of infusion; min = minutes; h = hours; SCR = screening.

^{* =} only on Cycle 2; ** = every fourth cycle (e.g Cycle 4, Cycle 8, Cycle 12 etc.)

Page 21 of 127 Version: 2.0 Date: 22 JAN 2024

Table 4: Schedule of activities and procedures – Randomized Phase II; control arm (mFOLFIRINOX)

Treatment cycle (14 d)	SCR 2	Cycle 1		Cycle 2		Су	rcle 3	(Cycle 4-12	!	EOT 3	Safety FU 4	Survival FU ⁵
Days ¹		1	1	3	8	1	3	1	3	8		Š	Su
Informed consent ⁶	X												
Eligibility	X												
Medical history 7	X												1
TB screening ⁸	X												
DPD deficiency screening ⁹	X												
UGT1A1 mutation screening ¹⁰	Х												
Demographics	Х												
Height	Х												
Weight ¹¹	Х	Х	Х			Х		Х			Х		
Physical examination	Х												
Symptom-directed exam 12		Х	X	[X]	[X]	X	[X]	Х	[X]	[X]	X		1
Vital signs ¹³	X	Х	X	X	X	X	Х	Х	X	X	X	X	1
Performance status 14	X	Х	Х			Х		Х			Х		
HRQoL ¹⁵	Х					X		[X]			X		X
Concomitant medications 16	Х	Х	X	Х	Х	X	Х	Х	Х	Х	X	X	
Adverse events 17		Х	X	Х	Х	X	Х	Х	Х	Х	X	X	
ECGs 18	Х	X	X			X		[X]			Х		
Hematology 19	Х	Х	X			X		Х			X	X	
Chemistry ²⁰	Х	Х	X			X		Х			X	X	
Serum amylase ²¹		X	Х			Х		Х			Х		

Page 22 of 127 Version: 2.0 Date: 22 JAN 2024

Treatment cycle (14 d)	SCR 2	SCR 2	SCR 2	Cycle 1		Cycle 2		Су	rcle 3	(Cycle 4-12		EOT 3	Safety FU 4	Survival FU ⁵
Days ¹		1	1	3	8	1	3	1	3	8	1	ű	Su		
Serum lipase ²¹		X	Х			Х		Х			X				
Haptoglobin ²¹		Х	Х			Х		Х			X				
GGT ²²	Х	Х	Х			X		Х			Х				
Urinalysis ²³	Х														
Urine pregnancy test 24	Х	Х	Х			Х		Х			X				
CA19-9 ²⁵	Х	Х		Х	X		Х	[X]**	X**		X		Х		
Disease assessment ²⁶	Х							Х			Х		X		
ADCC, CDC, and cytokines ²⁷		Х		Х	Х				X	X					
Tumor biopsy ²⁸	Х										[X]				
ctDNA ²⁹		Х						[X]			X		[X]		
Randomization ³⁰	X 30														
mFOLFIRINOX administration 31		Х	Х			Х		Х							
Survival status ⁵													Х		

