3 OBJECTIVES AND ENDPOINTS

OBJECTIVES	ENDPOINTS
	PRIMARY
	Phase I
To assess the safety and identify the RP2D of BNT321 in combination with	The proportion (%) of patients who received at least one dose IMP reporting:
mFOLFIRINOX as adjuvant therapy in patients with R0 or R1 resected PDAC.	 Incidence and occurrence of TEAEs including Grade ≥3, serious, fatal TEAE by relationship.
	 Occurrence of DLTs within a cohort during the DLT evaluation period.

^{*}Source: Conroy et al. 2018, PRODIGE 24-ACCORD.

Page 41 of 127 Version: 2.0 Date: 22 JAN 2024

OBJECTIVES	ENDPOINTS
Phase II	
To assess the efficacy of mFOLFIRINOX + BNT321 versus mFOLFIRINOX alone as adjuvant therapy in PDAC patients post R0 or R1 resection by mDFS.	In patients who are randomized into the trial: DFS defined as the time from randomization to occurrence of any of the following: • Locoregional recurrence or distant metastasis as determined by an independent central radiology assessment. • Occurrence of second primary (same or other) cancer as determined by an independent central radiology assessment. • Death from any cause.
	SECONDARY
I	Phase I and II
To further assess the efficacy of mFOLFIRINOX + BNT321 or mFOLFIRINOX as adjuvant therapy in PDAC patients post R0 or R1 resection by OS.	In patients who are enrolled/randomized into the trial: OS is defined as the time from first dose of trial treatment to death from any cause.
To further assess the efficacy of mFOLFIRINOX + BNT321 or mFOLFIRINOX as adjuvant therapy in PDAC patients post R0 or R1 resection by RFS and DFS rates.	In patients who are enrolled/randomized into the trial: RFS is defined as the time from randomization to occurrence of any of the following events, whichever occurs first: • Locoregional recurrence or distant metastasis as
	determined by the investigator. Death from any cause.
To characterize the PK of BNT321 when co- administered with mFOLFIRINOX.	In patients who are dosed with at least one dose of IMP and who have evaluable PK data: • PK parameters derived from serum concentration of IMP, including mean AUC, mean C _{max} , and median t _{max} in Cycles 2 and 3 followed by sparse sampling through EOT.
To characterize immunogenicity of BNT321 when co-administered with mFOLFIRINOX.	In patients who are dosed with at least one dose of IMP: • Percentage of patients with detectable ADA formation in Cycles 1 and 3, followed by sparse sampling through EOT.

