8.8 Immunogenicity assessments

Immunogenicity samples will be collected from all patients on the combination therapy arm (will not be collected for the control arm). Planned time points for immunogenicity sampling (anti-BNT321 antibodies) are provided in the SoA (Section 1.3). An extra sample will be taken for re-testing of future analysis if required. Samples will also be collected at the final visit from patients who discontinued trial treatment or were withdrawn from the trial.

Samples and any data derived using the collected samples will be processed in compliance with the applicable regulations and GCP.

Blood samples for immunogenicity analysis must be collected, handled, frozen and shipped as outlined in the laboratory manual.

Page 83 of 127 Version: 2.0 Date: 22 JAN 2024

Immunogenicity samples will be analyzed by a specialty laboratory. All collection and storage tubes will be provided in the laboratory sampling kits.

Leftover of samples collected for PK testing and of samples collected for immunogenicity testing can be used interchangeably if they were collected at the same timepoint and after the original purpose of the sample was fulfilled.

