Individual and mean (\pm standard deviation) serum concentration of BNT321 when coadministered with mFOLFIRINOX will be tabulated and plotted over time. PK parameters will be estimated from the serum concentration data using a non-compartmental analysis method. PK parameters will include C_{max} , t_{max} , $t_{1/2}$, Vd, AUC, and CL. These parameters will be listed by individual patient and summarized using descriptive statistics (means, medians, ranges, standard deviations, and coefficient of variation as appropriate).

Immunogenicity

The immunogenicity analysis will be performed based on FAS.

Immunogenicity results will be listed by patient, and a summary will be provided by the number and percentage of patients who develop detectable anti-BNT321 antibodies. The immunogenicity titre and neutralising ADA data will be listed for samples confirmed positive for the presence of anti-BNT321 antibodies.

The effect of immunogenicity as well as the effect of its neutralising properties on PK, pharmacodynamics, efficacy, and safety will be evaluated, if the data allow.

Pharmacodynamic (PD)

The PD analysis will be performed based on Pharmacodynamic Set (PD Set).

The percentage of lysis of target positive cells via patient-derived effector cells as a readout for ADCC activity, and/or patient-derived serum containing antibody and/or complement as a readout for CDC activity will be summarized by visit. Other PD parameters may be summarized if sufficient data is available.

Page 91 of 127 Version: 2.0 Date: 22 JAN 2024

Heath-related quality of life (EORTC QLQ-C30 and QLQ-Pan26)

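### The immunogenicity analysis uses the FAS and the endpoint counts Cycle 1 positivity as ADA formation; an ADA-evaluable set and a treatment-emergent definition are needed, and Phase II ADA sampling is thin after C6D1

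*Combined protocol and SAP*

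**What the plan says.** **Endpoint.** Section 3 (repeated in the synopsis) lists immunogenicity as a secondary endpoint for both phases, in patients given at least one dose of IMP: "Percentage of patients with detectable ADA formation in Cycles 1 and 3, followed by sparse sampling through EOT".

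**Analysis.** Section 9.5.3 states: "The immunogenicity analysis will be performed based on FAS". Section 9.4 defines the FAS as everyone randomized. It defines separate evaluable sets for PK and PD, but none for ADA. Section 9.5.3 summarizes patients who develop antibodies and adds: "The effect of immunogenicity as well as the effect of its neutralising properties on PK, pharmacodynamics, efficacy, and safety will be evaluated". That last analysis is conditional on adequate data.

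**Who is sampled, and when exposure starts.** Section 8.8 has ADA samples taken in the combination arm and says they "will not be collected for the control arm". Section 6.3 starts BNT321 in Cycle 2, by default on C2D3.

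**Phase II sampling times.** Table 2 footnote 29: "Anti-drug antibodies will be measured from blood collected prior to dosing of mFOLFIRINOX on C1D1, C3D1, C6D1, and at EOT". The Table 2 grid shows no ADA draw in Cycles 13 to 24. For PK, footnote 27 says: "For a full pharmacokinetic profile and in-depth sampling, blood will be collected on C2D3 and C3D3". It adds that from Cycle 4 trough and peak samples "will be drawn on day of BNT321 administration". The Table 2 grid and Table 3 add C2D8, limit the later PK draws to every fourth cycle, and show no PK at EOT.

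**The concern.** An ADA incidence is interpretable only if the denominator is patients who were exposed and then tested, and if antibodies present before exposure are kept apart from those that arise after it. The plan does neither. Its analysis set is defined by randomization, which is the wrong filter here: it leaves out every Phase I patient and brings in patients who could never show treatment-emergent ADA. Its endpoint wording treats a sample taken before any BNT321 as a time at which antibodies form.

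The secondary issue is timing. The plan intends to relate ADA to PK, but in Phase II most of the BNT321 course passes with no ADA sample. The onset and persistence of antibodies in that span cannot be recovered later.

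**Working it through.** The plan gives no ADA rate or sample size, so there is no figure to reproduce. I set the definitions side by side and converted visits to nominal study days.

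**1. Who is in the FAS**

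| Group | BNT321 exposed | Post-BNT321 ADA result | In FAS |
|---|---|---|---|
| Phase I (about 20) | yes | planned | no, never randomized |
| Phase II control (about 150) | no | none | yes |
| Combination, no BNT321 dose | no | none possible | yes |
| Combination, dosed, no later ADA result | yes | none | yes |
| Combination, dosed, later ADA result | yes | yes | yes |

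The third row includes patients who stop before C2D3. It also includes those randomized but never treated: Section 7.4 replaces them, but they remain randomized. Only the last row belongs in a Phase II incidence, and the first row is missing although the endpoint covers it.

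**2. Effect on the combination-arm rate**

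Let p be the true incidence among evaluable patients and d the share of the 150 combination patients who are not evaluable. Reported rate = p × (1 − d). The documents give neither p nor d; the ranges are assumptions.

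| p | d = 0% | d = 10% | d = 20% |
|---|---|---|---|
| 5% | 5.0% | 4.5% | 4.0% |
| 10% | 10.0% | 9.0% | 8.0% |
| 20% | 20.0% | 18.0% | 16.0% |

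Example: with d = 20%, 120 patients are evaluable; p = 10% gives 12 positives, and 12/150 = 8.0%.

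**3. The Cycle 1 sample**

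Day = (cycle − 1) × 14 + day of cycle. C1D1 = 1 and C2D3 = 17, so C1D1 precedes first exposure by 16 days (14 if BNT321 is given on C2D1). A C1D1 positive is therefore pre-existing reactivity. Each one counted as ADA formation adds 1/150 = 0.67 percentage points to the arm's rate.

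The baseline definitions do not settle this. Section 9.5.1 takes the last value before randomization in Phase II, whereas Section 3 takes the last value before trial treatment. Randomization may fall between Day −3 and C1D1, so the C1D1 ADA sample may come after it and fail the Section 9.5.1 definition.

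**4. Phase II timing**

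- ADA: C1D1 = 1, C3D1 = 29, C6D1 = 71, then EOT (about day 337 after 24 cycles).
- PK, default Day 3 dosing: C2D3 = 17, C2D8 = 22, C3D3 = 31, C4D3 = 45, C8D3 = 101, and on to C24D1 = 323.
- Shared days: none. C3D1 is 31 − 29 = 2 days before C3D3. C6D1 is 71 − 45 = 26 days after C4D3 and 101 − 71 = 30 days before C8D3.
- C6D1 to EOT: 337 − 71 = 266 days, or 38 weeks.
- BNT321 doses in Cycles 2 to 24: 23. Four (C2 to C5) precede C6D1; 19 follow it, and 19/23 = 83%.
- Phase I comparison: additional draws at C9D1, C12D1, C18D1 and C24D1 (days 113, 155, 239, 323), with a longest gap of 84 days.

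**5. Alternative readings**

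- Day 1 dosing with Table 3: C3D1 coincides with PK; C6D1 does not.
- Day 1 dosing with footnote 27 read as every cycle: C3D1 and C6D1 both coincide.
- Day 3 dosing with footnote 27 read as every cycle: no shared day, but C6D3 is only 2 days after C6D1.

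**The case against.** **Control arm.** A reader might infer that the control arm halves the reported rate. The documents do not support this. Section 9.5.1 presents Phase II by treatment group, so the unsampled arm need not be pooled. What remains is the unexposed or untested patients within the combination arm.

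**Cycle 1.** Section 9.5.3 counts patients who develop antibodies, and C1D1 is the necessary pre-exposure reference, so an analyst could handle it correctly. Section 9.5 also leaves technical detail to a SAP finalized before the first database lock. This softens the point but does not remove it: no treatment-emergent rule is written, and the Section 3 wording points the other way.

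**Timing.** A reader might infer that ADA and PK can never be matched in Phase II, or that incidence and the effect on PK are not derivable. Neither follows.
- The Day 1 option, if adopted, makes C3D1 coincide with PK.
- On Day 3 dosing, C3D1 can be set against the C3D3 profile, with no BNT321 dose between the ADA draw and the pre-infusion sample.
- In completers, EOT follows the C24D1 trough by about 14 days, so those two can be compared.
- Section 8.8 also asks for a final-visit sample from patients who discontinue.
- A cumulative proportion from C3D1, C6D1 and EOT can be computed.

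The analysis of ADA effects is itself conditional, the endpoint announces sparse sampling, and the rationale calls Phase II PK and PD work limited. Phase I supplies matched draws at C18D1 and C24D1, though in only about 20 patients. Thinner Phase II sampling is a legitimate design choice.

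**Sharing leftovers.** A reader might infer that Sections 8.5 and 8.8 already allow ADA testing on PK samples. They allow interchange only where both samples were taken at the same time point, and Section 8.10 requires both assessments to be in the schedule of activities. From C8 to C24 no ADA sample is scheduled to share with.

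**Conclusion.** The analysis-set and definition point holds. As written, Section 9.5.3 conflicts with the endpoint population in Section 3, supplies no Phase I patients for an endpoint covering both phases, and lets unexposed or untested combination patients lower the rate. For a true incidence of 10% the reported figure would be 10.0% to 8.0%, assuming 0% to 20% of 150 patients are not evaluable. In Phase I the loss is total, because the set is empty. Pre-existing and treatment-emergent positivity are not separated.

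The timing point is secondary and more debatable. On the default Day 3 schedule, a completer has no ADA sample for about 38 weeks and 19 of 23 planned BNT321 doses. Onset, persistence and mid-course ADA-PK pairing are lost; cumulative incidence and the two near-paired comparisons are not.

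This is a descriptive secondary endpoint. Nothing here touches the primary DFS test or its error rate.

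**What to change.** **Main change (Sections 9.4, 9.5.3 and 3, and the synopsis).**
- Replace the FAS for immunogenicity with an ADA-evaluable set: Phase I patients and Phase II combination patients with at least one BNT321 dose and at least one ADA result after it. Name BNT321 rather than IMP, because the Section 6 definition of IMP also covers reference products.
- Report C1D1 positivity as baseline prevalence, stating that the reference is the last sample before the first BNT321 dose.
- Report treatment-emergent ADA separately, with a written rule for patients already positive, or without a result, at C1D1.
- Remove Cycle 1 from the ADA-formation wording in Section 3.

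The cost is wording only. Section 9 lets the SAP modify the outlined analyses where appropriate, so the set and definitions can go there; the Section 3 text should be aligned at the next amendment.

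**Optional change (Table 2 and footnote 29).** Add ADA to some existing pre-infusion PK draws, for example C8, C12, C16, C20 and C24. Reword the footnote, which ties ADA draws to mFOLFIRINOX dosing, and reconcile footnote 27 with Table 3 on PK frequency. No new visit is needed. Section 4.1.3 does not expressly list ADA timing among its adaptive elements, so plan an amendment before Phase II sampling starts. The downside is added assay cost and possibly an extra tube, which must fit the 115 mL per-cycle limit in Section 8.10.

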ADCC	Antibody-dependent cell-mediated cytotoxicity
CA19-9	Sialyl-Lewis A (sLe ^a) antigen
CnDn	Cycle number day number
CRO	Contract research organization
CT	Computed tomography
DCO	Data cut-off
DFS	Disease-free survival
DLT	Dose-limiting toxicity
eCRF	Case report form
ECG	Electrocardiogram
ECOG	Eastern Cooperative Oncology Group
EDC	Electronic data capture (system)
EOT	End of treatment
Eol	End of infusion
FFPE	Formalin-fixed paraffin-embedded tissue
FOLFIRINOX	Leucovorin, 5-fluorouracil (5-FU), irinotecan, and oxaliplatin
FU	Follow-up
GGT	Gamma-glutamyl transferase
HRQoL	Health-related quality of life
CCI	
IB	Investigator's brochure
IDMC	Independent data monitoring committee
IMP	Investigational medicinal product
IRR	Infusion-related reactions
ITT	Intent to treat
IWRS	Interactive web response system
KPS	Karnofsky performance status
LFT	Liver function test
MCH	Mean corpuscular hemoglobin
mDFS	Median disease-free survival

Page 31 of 127 Version: 2.0 Date: 22 JAN 2024

Abbreviation/Term	Explanation
MRI	Magnetic resonance imaging
MTD	Maximum tolerated dose
NCI CTCAE	National Cancer Institute common terminology criteria for adverse events
OS	Overall survival
PDAC	Pancreatic ductal adenocarcinoma
PD	Pharmacodynamics
PFS	Progression-free survival
PK	Pharmacokinetics
POCBP	Patient of childbearing potential
RBC	Red blood cell
RCP	Royal College of Pathologists
RP2D	Recommended Phase 2 dose
SAE	Serious adverse event
SAP	Statistical analysis plan
SoA	Schedule of activities
SoC	Standard-of-care
SOC	System organ class
SRC	Safety review committee
ТВ	Tuberculosis
TEAE	Treatment-emergent adverse events
UGT1A1	UDP glucuronosyltransferase family 1 member A1
WBC	White blood cell

Page 32 of 127 Version: 2.0 Date: 22 JAN 2024

2 INTRODUCTION

2.1 Trial rationale

For early stage, non-metastatic PDAC, complete surgical resection can result in cure for some patients. mFOLFIRINOX is currently adapted as an adjuvant therapy for resectable PDAC, however, relapse in this setting is common, with a 3-year disease-free survival (DFS) realized in less than 40% of patients (Conroy et al. 2018). Improved PDAC adjuvant treatment options are therefore a high priority for clinical development.

BNT321-02 is planned as a Phase I/II clinical trial to evaluate the safety, multicycle tolerability, and efficacy of mFOLFIRINOX ± BNT321 as a novel combination adjuvant therapy for patients with R0 or R1 resected PDAC. The Phase I part of this trial will determine the safety and BNT321 recommended Phase II dose (RP2D) together with chemotherapy for previously untreated patients who are eligible to receive 24 weeks of PDAC adjuvant therapy. A key secondary pharmacodynamic endpoint in Phase I is determining the extent of complement-dependent cytotoxicity (CDC) and antibody-dependent cellular cytotoxicity (ADCC) effects in peripheral blood longitudinally over an extended adjuvant therapy course. The safety and feasibility of continuing BNT321 monotherapy for 24 weeks beyond the initial 24 weeks of combination treatment will also be determined.

The BNT321-02 randomized Phase II part of this trial is a dedicated evaluation of the potential for mFOLFIRINOX + BNT321 combination therapy to provide meaningful clinical benefit over standard adjuvant mFOLFIRINOX. The Phase II part is designed to detect a substantial increase in median disease-free survival (mDFS), specifically with a target 36 months mDFS which represents more than 12 months improvement over current chemotherapy. Overall survival (OS) is a secondary endpoint for the Phase II, and demonstrated improvements will provide additional evidence of clinical benefit and further support the performance of additional follow-on trials in PDAC. Additional evaluations are limited pharmacokinetic and pharmacodynamic (ADCC, CDC, circulating tumor DNA [ctDNA], and CA19-9) assessments, which may help further characterize the clinical benefit and allow for more tailored designs in follow-on BNT321 trials.

For a rationale for the trial design, see Section 4.2.

For the rationale for the dosing regimen, see Section 6.2.

